Objectives	The primary objective of this study is to determine if physical exam indicated cerclage use reduces the incidence of spontaneous PTB in asymptomatic women with twin gestations with cervical dilation diagnosed on pelvic exam before 24 weeks of gestation.
Number of Subjects	52
Diagnosis and Main Inclusion Criteria	Women, age older than 18, with a twin gestation and cervical dilation on pelvic exam and/or visible membranes on speculum exam between 16 to 23 6/7 weeks gestation
Study Product and Planned Use	Cervical cerclage
Reference therapy	Standard obstetrical expectant management
Statistical Methodology	Statistical analysis will be based on the intention-to-treat principle. The risk of spontaneous preterm birth before 34 weeks will be quantified by use of the odds ratio and 95% CI. Multivariate analysis will be performed using logistic regression.

Definitions

PPROM: Preterm premature rupture of membranes, rupture of the amniotic membranes prior to 37 weeks of gestation.

PTB: Preterm birth: Birth prior to 37 weeks.

LBW: Low birth-weight infants, birth weight less than 2500 grams

Perivable gestational age: gestational age around 23-26 weeks of gestation, associated with high neonatal morbidity and mortality and high risk of neurodevelopmental delay.

Cervical dilation: any quantifiable uterine cervical opening by speculum or digital exam, if dilation progresses, it is associated with delivery of the fetus

Amniocentesis: is a surgical procedure for obtaining a sample of amniotic fluid from the amniotic sac in the uterus of a pregnant woman by inserting a hollow needle through the abdominal wall under continuous ultrasound guidance; it is used in diagnosing certain genetic defects or intrauterine infections.

Amnioreduction: consist of the removal of variable amount of amniotic fluid by amniocentesis

Cervical cerclage is a suture/tape surgically placed around the cervix as close as possible to the high of the internal os. This suture is a non-absorbable sterile material and needs to be removed later on before delivery

1 Introduction

This document is a protocol for a human research study.

1.1 Background

The incidence of preterm birth (PTB) in the United States is 12% with more than 500,000 deliveries occurring at less than 37 weeks gestation annually, however the incidence of early preterm (less than 34 weeks) remains unchanged at 3.4% being this the most vulnerable neonatal group.¹ Risk factors for spontaneous preterm births include a previous preterm birth, multiple pregnancies, black race, smoking, periodontal disease, low maternal body-mass index and short cervical length.²

In 2010, the twin birth rate was 33.1 twins per 1000 total births. The twin birth rate increased steadily by 76% overall from 1980 to 2009. The number of twin births has risen substantially due to the increased use of assisted reproductive technology. Twin pregnancies have 50% incidence of PTB, 10 times more at risk of low birth-weight infants (LBW) and had 5 times more risk of early neonatal death.³ The increased rate of PTB in twins is associated with increased neonatal morbidity and mortality rates. Disorders related to short gestation and LBW is the second cause of infant death (17.2%).¹

In singleton pregnancies with risk factors for PTB, effective medical interventions have been identified to reduce the risk of recurrent PTB. For women with prior PTB: weekly treatment with intramuscular 17-alpha hydroxyprogesterone caproate beginning at 16-20 weeks gestation until 36 weeks⁴ and cervical length surveillance from 16 to 24 weeks and ultrasound indicated cervical cerclage for women with cervical length less than 25mm before 24 weeks of gestation.⁵ For women with no prior PTB and incidental finding of cervical length less than 20mm before 23 weeks of gestation will benefit from vaginal progesterone⁶ or pessary.⁷ Similar to singleton pregnancies, short cervical length less than 25mm before 24 weeks in twins pregnancies predicts preterm birth,^{8,9} however, treatment with 17-alpha hydroxyprogesterone caproate,¹⁰ vaginal progesterone^{11, 12} or ultrasound indicated cervical cerclage¹³⁻¹⁵ were not effective in reducing the rate of PTB in women with twin gestations. There are small trials, subgroup analyses, and a meta-analysis suggesting that vaginal progesterone and the Arabin cervical pessary may reduce rates of preterm birth in twins of mothers with a short cervix but this information has not been confirmed.^{16, 17}

The identification of cervical dilation during the second trimester is a rare event but represents the worst prognostic factor for PTB in both singleton and twin gestations. This finding is independent of other risk factors, especially if the amniotic membranes are exposed to the vaginal environment; this presentation is associated with a 90% rate of PTB in singletons.¹⁸⁻²² Physical-exam indicated cerclage between 14 to 26 weeks in singleton pregnancies decreased PTB < 28 weeks by 92% and <32 weeks by 64% in prospective cohorts, it decreased neonatal morbidity and 10-fold increase in neonatal survival when compared with expectant management.¹⁹⁻²⁴ There are few case reports of twin pregnancies with cervical dilation were physical exam indicated cerclage outcomes were similar to those in singleton pregnancies.²⁵⁻²⁸ The current management of women with twin pregnancies, dilated cervix and visible amniotic membranes is expectant management. There is no current information whether physical exam

indicated cerclage would prolong pregnancy and decrease the risk of preterm birth, especially in the very preterm birth group.

Our primary hypothesis in performing this study is that the use of a physical exam indicated cerclage in women with asymptomatic cervical dilation before 24 weeks will prolong pregnancy and will decrease the incidence of PTB less than 34 weeks gestation when compared with expectant management.

1.2 Clinical Data to Date

A retrospective review of 12 women with twin pregnancies who underwent a physical exam-indicated cerclage (dilated cervix on examination or membranes visible at the external cervical os on speculum examination) during the second trimester were compared with 31 singleton pregnancies undergoing the same procedure from 1997 to 2012.²⁵ Comparing twins to singletons, the median time from cerclage placement to delivery was similar (92 vs. 106 days, p=0.3), as was the median GA at delivery (33.5 vs. 35.0 weeks, p=0.2). The likelihood of delivery at >32 weeks (75.0% vs. 71.0%, p>0.9) and the likelihood of neonatal survival to discharge (83.3% vs. 83.9%, p>0.9) were also similar. A case report of 4 women with twin pregnancy and cervical dilation with bulging membranes gave birth on an average of 48.5 days after cerclage placement.²⁶ A more recent publication evaluated 104 women with twin pregnancy vs. 334 singleton pregnancies with dilated cervix, median gestation at delivery was (31.9 weeks vs. 32.7 weeks) and delivery before 28 weeks (33.7% vs. 35.8%, P = .69) respectively.²⁸ **None of these publications have had an appropriate control group: twin gestation with expectant management.** Only one small retrospective cohort study had a control group with expectant management,²⁷ 23 women were identified with twin pregnancy, cervical dilation and visible membranes between 16-24 weeks; 16 underwent physical exam indicated cerclage while 7 received expectant management (control). In the control group 50% of the women were delivered prior to 24 weeks. Interval from time at diagnosis to delivery was significantly prolonged by approximately 6.8 weeks in the cerclage group, they had significant decreased SPTB ≤28 weeks (31.2% vs. 85.7% p=0.02) and increased neonatal survival upon discharge 71.8% vs. 42% (p=0.1).

1.3 Risk/Benefits

Major risks of physical exam indicated cerclage that have been reported in previous studies involving singleton pregnancies and include intraoperative rupture of membranes between 4% and 15%, cervical laceration, bleeding, chorioamnionitis (undiagnosed at the time of cerclage or acquired posteriorly to its placement due to exposed membranes into the vaginal flora), failure to place the cerclage due to advanced cervical dilation and failure of the cerclage on prolonging pregnancy with possible pregnancy loss or delivery at a perivable gestational age around 23-26 weeks of gestation.^{23, 24, 29-32} Other risks of cerclage are those associated with anesthesia during the surgical procedure: hypotension, allergy to medications, post spinal headache. After the cerclage placement other risks maybe present during the following weeks as preterm contractions with the cerclage in place may cause laceration of the cervix and bleeding or preterm premature rupture of membranes in which case the cerclage needs to be removed.

Minor side effects include increased noninfectious vaginal discharge: there is a theoretical disruption the vaginal flora associated with foreign object, and minimal discomfort at the time of cerclage removal.

The potential benefits include prolongation of pregnancy, decreasing very preterm delivery (< 28 weeks), very low birth weight (<1500 grams), low birth weight (<2500 grams) and decreased neonatal morbidity (admission to the intensive care unit, respiratory distress, need of intubation, necrotizing enterocolitis, intraventricular hemorrhage), neonatal mortality and long term disease or disability associated with prematurity. These potential benefits are based on results of previous retrospective cohorts of available research in singletons and case reports in twin pregnancies. These benefits significantly outweigh the risk of having a complication related to cerclage placement.

Measurement to decreased risks associated to the cerclage: All of the investigators have received formal training on physical exam indicated cerclage placement. The training and experience of the investigators will minimize the risks associated with cerclage placement.

Our protocol specifically states that the cerclage will be removed if the patient has persistent preterm contractions associated labor, has premature preterm rupture of membranes (PPROM), presents with active cervical bleeding or if she remains asymptomatic and reaches 36 weeks of gestation.

2 Study Objectives

The overall objective of this study is to assess the efficacy of the use of a physical exam indicated cerclage for prevention of PTB in a population of women with twin gestations, dilated cervix and visible membranes at the time of speculum exam between 16 0/7 to 23 6/7 weeks.

2.1 Primary Objective

The primary objective of this study is to determine if physical exam indicated cerclage reduces the incidence of spontaneous PTB before 34 weeks in asymptomatic women with twin gestations, dilated cervix and visible membranes diagnosed on pelvic exam between 16 0/7 to 23 6/7 weeks of gestation.

2.2 Secondary Objective

To determine if cerclage reduces the incidence of spontaneous PTB <28 weeks and <32 weeks in asymptomatic women with twin gestations and dilated cervix diagnosed on pelvic exam between 16 to 23 6/7 weeks of gestation

To determine if cervical cerclage reduces the incidence of neonatal admission to the neonatal intensive care unit, decrease length of stay in the neonatal intensive care unit, decrease neonatal disease or death associated with prematurity in asymptomatic women with twin gestations, dilated cervix and visible membranes diagnosed on pelvic exam between 16 to 23 6/7 weeks of gestation

3 Study Design

3.1 General Design

This is a multi-center, open-label, randomized study. Women with twin gestations that have dilated cervix (1-5cm) with visible membranes during ultrasound, pelvic exam and/or speculum exam will be invited to participate in the trial.

3.2 Primary Study Endpoints

Spontaneous preterm delivery at less than 34 weeks gestation

3.3 Secondary Study Endpoints

Secondary effectiveness endpoints:

- Gestational age at delivery
- Interval between diagnosis and delivery
- Birth weight of each neonate
- Spontaneous preterm birth rates at less than 24, 28, 32 and 37 weeks gestation
- Spontaneous rupture of membranes before 34 weeks gestation

Secondary safety endpoints:

- Admission to the NICU and length of stay
- Neonatal death before discharge
- Composite adverse neonatal outcome (includes necrotizing enterocolitis, Intraventricular hemorrhage (grade 2 or higher), respiratory distress syndrome, retinopathy, treatment for sepsis and neonatal death)
- Chorioamnionitis (clinical or histological)
- Significant adverse maternal effects including intraoperative rupture of membranes, bleeding and cervical laceration (tear).

4 Subject Selection and Withdrawal

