7.1 Sample Size Determination

Calculation of sample size was based on a reduction in the incidence of spontaneous delivery before 34 weeks from 80% in the expectant management group to 40% in the cerclage group, with a power of 80%. To detect this difference at a significance level of 5%, we will need to enroll a total of 46 subjects with 23 subjects in each arm, plus 10% for loss of follow up. Total 52 subjects with 26 subjects in each arm

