7.2 Statistical Methods

The primary outcome is spontaneous preterm birth before 34 weeks of gestation. Secondary outcomes include gestational age at delivery, interval between diagnosis and delivery, birth weight, spontaneous preterm birth rates at less than 24, 28, 32 and 37 weeks gestation, clinical chorioamnionitis and spontaneous rupture of membranes at less than 34 weeks gestation. Secondary safety outcomes include admission to NICU, neonatal death, length of stay in the NICU until discharge home, composite adverse neonatal outcome that includes necrotizing enterocolitis, intraventricular hemorrhage (grade 2 or higher), respiratory distress syndrome, retinopathy of prematurity and treatment for sepsis), and significant adverse maternal effects will include: intraoperative rupture of membranes, chorioamnionitis, postpartum hemorrhage (estimated blood loss and requirement of blood transfusion, cervical tear and uterine rupture).

Statistical analysis will be based on the intention-to-treat principle.

Comparisons between the two groups will be made with the Mann-Whitney U test. Univariate comparisons of dichotomous data will be performed with Fishers exact test. The p values for all hypotheses will be two sided, and p values of less than 0.05 will be considered to be significant. The risk of spontaneous preterm birth before 34 weeks will be quantified by use of the relative ratio and 95% CI. Multivariate analysis will be performed using logistic regression. The risk of spontaneous preterm birth from randomization until 34 weeks will be assessed with Kaplan-Meier analysis, in which gestational age

is the timescale, spontaneous delivery is the event, and elective deliveries are censored. SPSS software package (version 16.0) will be used for all statistical analyses.

8 Safety and Adverse Events

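### Birth weight has no rule for pregnancy losses: as worded, the comparison appears limited to neonates, which selects on a post-randomisation outcome and costs power

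*Combined protocol and SAP*

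**What the plan says.** Section 3.3 places "Birth weight of each neonate" among the secondary effectiveness endpoints. Section 7.2 restates it without the word neonate ("Secondary outcomes include gestational age at delivery, interval between diagnosis and delivery, birth weight") and gives the test: "Comparisons between the two groups will be made with the Mann-Whitney U test". The same section adopts intention to treat. Neither section names the population for birth weight or a rule for a fetus that is lost before viability or stillborn. No SD, effect size or power is given for it.

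Section 4.1 admits women from 16 to 23 6/7 weeks. Section 1.3 names pregnancy loss as a possible outcome after cerclage and counts a reduction in "very low birth weight (<1500 grams), low birth weight (<2500 grams) and decreased neonatal morbidity" among the potential benefits. On the only cited twin cohort with an expectant-management group, section 1.2 says: "In the control group 50% of the women were delivered prior to 24 weeks". That group had 7 women.

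**The concern.** Read literally, a fetus delivered dead or before viability never becomes a neonate and contributes no birth weight. Keeping fetuses alive past that point is what cerclage is meant to do, so the omission would fall more heavily on the expectant arm. That arm would then be represented mainly by its longer pregnancies and the cerclage arm by a broader mix. These are no longer the groups that were randomised, which conflicts with the intention-to-treat statement in 7.2. A real benefit would be diluted. In an unfavourable pattern, small infants saved by cerclage would pull down that arm's weights.

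**Working it through.** **1. The plan's own figure.** Section 7.1 plans a change "from 80% in the expectant management group to 40% in the cerclage group, with a power of 80" per cent. With pooled variance, two-sided 5% and no continuity correction:

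n = [1.960·√(2·0.6·0.4) + 0.842·√(0.8·0.2 + 0.4·0.6)]² / 0.4² = (1.358 + 0.532)² / 0.16 ≈ 22.3, so 23 per arm and 46 in total. Then 46/0.9 = 51.1, so 52, or 26 per arm. The stated size reproduces. It concerns delivery before 34 weeks only.

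**2. Assumed delivery patterns.** The documents fix the 80% and 40% and cite the 50% before 24 weeks. Every other split below is an assumption. Each cell gives expectant/cerclage, in per cent of women.

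| Pattern | <24 wk | 24–28 | 28–34 | ≥34 |
|---|---|---|---|---|
| Planned A | 50/15 | 25/16 | 5/9 | 20/60 |
| Planned B | 50/20 | 20/11 | 10/9 | 20/60 |
| Shift C | 50/15 | 30/65 | 0/0 | 20/20 |
| Shift D | 50/15 | 20/45 | 10/15 | 20/25 |

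In all four, the share of women delivered by 24, 28 or 34 weeks is never higher with cerclage.

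**3. What selection does, by arithmetic.** Take live birth from 24 weeks. The share of live births at ≥34 weeks, expectant versus cerclage, is then:

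- A: 20/50 = 40% versus 60/85 = 71%
- B: 20/50 = 40% versus 60/80 = 75%
- C: 20/50 = 40% versus 20/85 = 24%
- D: 20/50 = 40% versus 25/85 = 29%

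In A, the gap of 40 points among all women shrinks to 31, and the women contributing fall from 26 and 26 to 26·0.50 = 13 and 26·0.85 ≈ 22. In C and D the order reverses although cerclage does no worse at any of these cut-points.

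**4. Simulation.** 26 per arm, one weight per woman, gestational age uniform within bands, assumed median weight rising from 620 g at 24 weeks to 2,700 g at 38 weeks, 12% log-SD, Mann-Whitney at two-sided 5%.

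| Live birth from | A, B: power, losses ranked lowest | A, B: power, live births only | C, D: live-only result favours expectant care |
|---|---|---|---|
| 24 weeks | about 82–90% | about 37–41% | about 76–77% of trials |
| 23 weeks | about 81–90% | about 54–55% | about 51–55% |
| 22 weeks | about 82–90% | about 61–66% | about 31–36% |

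Repeat runs with other assumed weight curves moved these by two or three points; live-only power over the 22- and 23-week cuts spans about 52–66%. Under A and B the live-only result favours expectant care in about 5% of trials with the 24-week cut (4–6% across runs), fewer with the others, and almost never significantly. Under C and D a significant reversal occurs in at most about 11% of trials (9–12% across runs with the 24-week cut).

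**5. Sensitivity to early loss.** A second model (23 per arm, 80%/40% before 34 weeks held fixed) compared weighing all births with live births only.

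| <24 wk, expectant/cerclage | All births | Live from 24 wk | Live from 22 wk |
|---|---|---|---|
| 50/10% | 91% | 28% | 62% |
| 50/20% | 77% | 36% | 57% |
| 50/25% | 64% | 41% | 55% |
| 30/10% | 73% | 46% | 57% |

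Ranking losses lowest gave 91%, 77%, 66% and 73%.

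**6. When could the planned effect itself reverse?** On the share reaching 34 weeks among births after 24 weeks, with L0 and L1 the expectant and cerclage proportions lost before then, reversal needs 0.20/(1−L0) > 0.60/(1−L1), that is L0 > 1 − (1−L1)/3. This is 67% at L1 = 0 and 70% at L1 = 10%, both above the cited 50%.

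**The case against.** The strongest reply is that the plan never restricts birth weight to live births. Section 7.2 says only birth weight, outcomes are abstracted from delivery records, and a stillborn or previable fetus can be weighed. The survival figures quoted in 1.2 even suggest an all-fetus denominator: 71.8% of 32 fetuses fits 23/32 = 71.9%, and 42% fits 6/14 = 42.9%, although 3/7 fits as well. This stands to a degree: live-born only is the natural reading of 3.3, not an explicit rule. If all births were weighed, the selection would disappear. The plan does not say that they will be.

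A reader might infer that more than half the power is lost under the planned effect. That needs live birth to start at 24 weeks and a large difference in early loss. The protocol itself describes the periviable period as beginning around 23 weeks, and with a 22- or 23-week cut less than half is lost.

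A reader might also infer that the trial is likely to show cerclage lowering birth weight. The reversing patterns have 80% versus 80% and 80% versus 75% before 34 weeks, almost no primary effect. They also sit badly with the cited 31.2% versus 85.7% at 28 weeks. They are possible, since 1.3 names periviable delivery after cerclage as a risk, but they are not what the plan expects.

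The 50% is weak too: half of 7 women is 3.5, not a whole number. Finally, gestational age at delivery, the interval to delivery and the preterm-birth rates can be obtained for every woman who delivers, and would be reported alongside.

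**Conclusion.** The concern holds as a gap in definition with a real bias behind it. As worded, the comparison appears to leave out losses, and the plan gives no rule that would bring them back. If they are left out, the arms compared are selected after randomisation and power falls in every pattern tried that meets the planned effect: from about 80–90% to about 37–41% (live birth from 24 weeks) or about 52–66% (from 22–23 weeks) at 50% control loss.

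Under the planned effect the sign is wrong in about 5% of trials or fewer. At 50% control loss, frequent reversal needs cerclage mainly to move losses into 24–28 weeks with little change at 34 weeks. It then occurs in about 31–77% of trials depending on the live-birth cut, and significantly in at most about 11%. With the planned effect held fixed, it would take control loss of roughly 70% or more.

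These sizes rest on assumed delivery splits and weight curves, and the main simulation gives both twins the same fate. The direction of the selection does not depend on the weight curve. The point touches one secondary endpoint with no power claim, not the primary result. It should be corrected because the correction is cheap.

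**What to change.** In 3.3 and 7.2, define the endpoint as birth weight over all fetuses of randomised women; a fetus lost or not born alive takes the lowest rank in the Mann-Whitney test, with one summary rank per woman. State how the two fetuses are combined, for example as the mean of their ranks. Report live-born weight by arm as descriptive only, with the number of live-born infants and the number of randomised fetuses beside it.

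Weighing every birth, dead or alive, would give nearly the same power, but needs a weight for each previable loss. Ranking losses lowest does not.

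The cost is wording: the test stays the same and no new data are needed. The downside is small: the p-value then refers to a ranked outcome that combines loss and weight, not to grams among the live-born.

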5.2.2 Expectant management

For those randomized to expectant management, they will continue routine pregnancy care.

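### The membrane-rupture effectiveness endpoint counts only spontaneous rupture, so on its plain reading it omits ruptures caused by the cerclage operation and tilts the comparison modestly toward cerclage

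*Combined protocol and SAP*

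**What the plan says.** Section 3.3 puts "Spontaneous rupture of membranes before 34 weeks gestation" among the secondary effectiveness endpoints. Section 7.2 keeps the restriction, naming "clinical chorioamnionitis and spontaneous rupture of membranes at less than 34 weeks gestation" among the secondary outcomes.

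Intraoperative rupture is placed elsewhere. Section 3.3 has it under safety, and in 7.2 the "significant adverse maternal effects will include: intraoperative rupture of membranes". Section 1.3 describes the major risks of the procedure as those "reported in previous studies involving singleton pregnancies and include intraoperative rupture of membranes between 4% and 15" per cent.

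The control arm has no planned operation: "For those randomized to expectant management, they will continue routine pregnancy care" (5.2.2). Rupture before randomization is an exclusion (4.2), so a rupture at surgery is always a post-randomization event. Section 7.2 specifies intention to treat and, for dichotomous data, Fisher's exact test, two-sided at 0.05.

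The Definitions section is broader than the endpoint: "PPROM: Preterm premature rupture of membranes, rupture of the amniotic membranes prior to 37 weeks of gestation". It has no restriction by cause. Nowhere do the documents define spontaneous for this endpoint, say how a woman ruptured at surgery is coded, or plan an analysis that combines the two kinds of rupture.

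**The concern.** A rupture at surgery is a consequence of assignment to cerclage. If the effectiveness endpoint excludes it, the cerclage arm loses events that the control arm has no way to lose, and the estimate moves toward cerclage. The separate safety item does not correct this. It is empty in the control arm by design, so it offers no comparison, and the Fisher test on the effectiveness endpoint is unchanged by it.

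The sign of the estimate is at stake. With no effect of cerclage on spontaneous rupture, the endpoint as worded leans toward benefit, while a count that includes procedure-related rupture leans toward harm. The trial is also open-label (3.1) and describes no adjudication, so a rupture soon after surgery would be called spontaneous or procedural by people who know the allocation.

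**Working it through.** **The plan's own figure.** The documents give no expected rate, power or sample size for this endpoint. The only related figure is the trial size in 7.1: 80% versus 40%, two-sided 5%, power 80%. The normal approximation with pooled variance and no continuity correction gives

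n per arm = [1.96 × √(2 × 0.6 × 0.4) + 0.8416 × √(0.8 × 0.2 + 0.4 × 0.6)]² / 0.4² = (1.358 + 0.532)² / 0.16 ≈ 22.3, rounded up to 23.

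That is 46 in total, and 46 / 0.9 = 51.1, rounded up to 52, or 26 per arm. The plan's figures reproduce and do not depend on the rupture endpoint.

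**Inputs for the rupture endpoint.**
- n = 26 per arm (7.1).
- r = intraoperative rupture rate, 4% to 15% (1.3, from singleton studies; assumed for twins).
- p = control rate of spontaneous rupture before 34 weeks. The documents give none; 30% is assumed, with a range of 20% to 60%.

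**Women affected.** 26 × 0.04 = 1.0 and 26 × 0.15 = 3.9. The chance of at least one is 1 − 0.96^26 = 65% and 1 − 0.85^26 = 99%. With 23 per arm the expected counts are 0.9 and 3.5.

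**Size of the artefact.** Suppose cerclage has no effect on spontaneous rupture in women not ruptured at surgery, and that women ruptured at surgery are not counted. Then:
- spontaneous-only rate, cerclage arm = p(1 − r), so the difference from control is −pr and the risk ratio is 1 − r;
- spontaneous or procedure-related rate, cerclage arm = r + p(1 − r), so the difference is +r(1 − p).

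| r | p (control) | Spontaneous only, cerclage | Difference | Spontaneous or procedural, cerclage | Difference | RR |
|---|---|---|---|---|---|---|
| 4% | 20% | 19.2% | −0.8 | 23.2% | +3.2 | 1.16 |
| 4% | 30% | 28.8% | −1.2 | 32.8% | +2.8 | 1.09 |
| 4% | 60% | 57.6% | −2.4 | 61.6% | +1.6 | 1.03 |
| 15% | 20% | 17.0% | −3.0 | 32.0% | +12.0 | 1.60 |
| 15% | 30% | 25.5% | −4.5 | 40.5% | +10.5 | 1.35 |
| 15% | 60% | 51.0% | −9.0 | 66.0% | +6.0 | 1.10 |

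Differences are in percentage points. The spontaneous-only risk ratio is 0.96 at r = 4% and 0.85 at r = 15%, whatever p is.

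**Effect on the test.** Enumerating both binomial counts at 26 per arm, over p = 20% to 60%, the chance of a significant Fisher result favouring cerclage is 1.1% to 1.4% with no artefact. It becomes 1.4% to 2.1% at r = 4% and 2.2% to 5.7% at r = 15%.

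**The case against.** The strongest reply is that nothing is hidden. Intraoperative rupture is a named safety outcome in the same section, a reader can add the two counts, and its consequences also reach gestational age at delivery, the interval to delivery and neonatal death. This stands as far as reporting goes. It does not repair the effectiveness comparison, which is the analysis the plan specifies.

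Several stronger readings are tempting, and the documents do not support them.

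- **A spurious benefit of 4 to 15 points.** A reader might assume equal total rupture of 30% in both arms and subtract the surgical ruptures, giving 30% versus 26% down to 15%. At the upper end, spontaneous rupture among women not ruptured at surgery would be 0.15 / 0.85 = 17.6% against 30%, so most of that gap is a real reduction in spontaneous rupture and not a product of the definition. In that scenario the chance of a significant result favouring cerclage would be 2.5% to 2.9% (r = 4%) or 12% to 22% (r = 15%), but those figures do not measure the artefact. The 4 to 15 points is the gap between the two definitions in the cerclage arm.
- **A stated rule that surgical ruptures are non-events.** There is no such rule. It is the plain reading of the word spontaneous together with the separate safety listing.
- **A woman ruptured at surgery can no longer rupture spontaneously.** Inclusion requires diamniotic twins (4.1), so a second sac could still rupture, and the endpoint does not say whether it counts women or sacs. If such later ruptures are counted, the artefact is smaller than the table shows.

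Two further points stand. The rupture rate is a singleton figure. Also, some women assigned to cerclage may not have the operation completed: 1.3 lists failure to place it and 5.2 allows withdrawal after randomization. Either could lower the count.

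**Conclusion.** The point holds and should be corrected, though it is not critical to the trial. As worded, the endpoint leaves treatment-caused ruptures out of an intention-to-treat comparison, and the omission runs in one direction only. About 1 to 4 of 26 cerclage women would be affected. The spurious benefit is 1.2 to 4.5 points at an assumed 30% control rate and 0.8 to 9 points over 20% to 60%. Counting procedure-related rupture would instead show an excess of 2.8 to 10.5 points at 30%.

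The conclusion rests on four assumptions: the singleton rupture rate applies to twins, all assigned women have the operation, surgical ruptures are coded as the plain reading suggests, and cerclage does not change spontaneous rupture in the remaining women. The problem is a misleading estimate on one secondary endpoint. A falsely significant result remains unlikely, and the primary endpoint and sample size are unaffected.

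**What to change.** In 3.3 and 7.2, define the endpoint per woman as spontaneous or cerclage-procedure-related rupture of membranes after randomization and before 34 weeks, excluding artificial rupture performed in labour or at delivery, analysed by intention to treat. Report spontaneous and intraoperative ruptures as components.

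The exclusion matters. Wording that took in rupture from every cause would also count artificial rupture in labour and at caesarean, and would turn the endpoint into something close to any delivery before 34 weeks.

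The cost is a wording change in two sections. Both components are already listed outcomes, so no new data or subjects are needed. Combining them also removes most of the unblinded judgement about whether a rupture soon after surgery was spontaneous. The downside for the sponsor is that the cerclage result on this endpoint becomes somewhat less favourable.
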